6.4 Visit 2 (Baseline)

Visit 2 (baseline) will be conducted a maximum of 14 days after the screening visit. The following will be assessed:

- Inclusion and exclusion criteria checked
- Pregnancy test, if applicable
- Recording of relevant medical history, including specific assessment of history of myocardial infarction, stroke, or congestive heart failure
- Recording of concomitant medication
- Physical examination (not performed later than the baseline visit)
- Measurement of height
- Measurement of weight
- Examination of vital signs
- ECG
- Safety laboratory tests
- Efficacy laboratory tests
- Treatment with iron isomaltoside
- AE evaluation and recording

6.5 Visit 3

Visit 3 will be conducted 2 weeks (± 2 days) after baseline. The following will be assessed:

- Changes in concomitant medication and medical history (worsening of symptoms or diseases shall be recorded as AEs)
- Examination of vital signs
- ECG
- Safety laboratory tests
- Efficacy laboratory tests
- AE evaluation and recording

6.6 Visit 4

Visit 4 will be conducted 13 weeks (± 3 days) after baseline. The following will be assessed:

- Changes in concomitant medication and medical history (worsening of symptoms or diseases shall be recorded as AEs)
- Examination of vital signs
- ECG
- Safety laboratory tests
- Efficacy laboratory tests
- AE evaluation and recording

6.7 Visit 5

Visit 5 will be conducted 26 weeks (± 4 days) after baseline. The following will be assessed:

- Changes in concomitant medication and medical history (worsening of symptoms or diseases shall be recorded as AEs)
- Physical examination
- Measurement of weight
- Examination of vital signs
- ECG
- Safety laboratory tests
- Efficacy laboratory tests
- AE evaluation and recording
- Completing the final visit form

7 TRIAL ASSESSMENTS

7.1 Demographic and Baseline Assessments

Date of birth, gender, race, ethnicity, and smoking habits will be collected. A current smoker is defined as a subject who has been smoking within the last 6 months.

7.2 Pregnancy Test

A urine pregnancy test will be performed for all women of childbearing potential. The test will be handled and interpreted by the site personnel.

7.3 Relevant Medical History

Relevant medical history will be recorded. Changes in medical history will be recorded at the subsequent visits during the trial (worsening of symptoms or diseases shall be recorded as AEs). The following will be collected: disease and start and stop date. Except for underlying disorder causing IDA, start dates occurring > 12 months before the enrolment into the trial should be set as > 12 months.

7.4 Concomitant Medication

If the subject is receiving any concomitant medication it will be recorded at the baseline visit. Changes in concomitant medication will be recorded in the subsequent visits during the trial. The following will be collected: generic name, indication, dose, and start and stop date. Start dates occurring > 12 months before the enrolment into the trial should be set as > 12 months.

7.5 Physical Examination

A physical examination will be performed based upon the Investigator's judgement and may include the following:

- Head-Eyes-Ear-Nose-Throat (HEENT)
- Cardiovascular system
- Respiratory system
- Nervous system
- Gastrointestinal system
- Musculo-skeletal system
- Urogenital system
- Dermatology system
- Others, if required

7.6 Height

Height will be measured.

7.7 Weight

Weight will be measured.

7.8 Vital Signs

Heart rate and blood pressure will be measured.

At the treatment visits, heart rate and blood pressure will be measured at the following time points during infusion of iron isomaltoside: approximately 0-10 minutes before infusion, during infusion, 5-15 minutes, and 20-40 minutes after the infusion has ended.

7.9 Electrocardiogram

A standard 12 lead ECG will be recorded (including date, time, and signature). At baseline, two ECGs will be recorded; one before administration of the trial drug and one approximately 30 minutes after start of the dosing. Only one ECG should be recorded at the follow-up visits.

The ECGs do not need to be evaluated by a cardiologist.

7.10 Laboratory Assessments

It is requested that the blood samples are drawn before administering the trial drug, and, if possible, that they are drawn at the same time of the day at all visits in order to reduce any diurnal fluctuation in the parameters.

Laboratory assessments will be performed at a central laboratory. A Laboratory Manual will be provided to each site in which all laboratory procedures will be described.

7.10.1 Eligibility Laboratory Assessments

The following eligibility laboratory assessments will be performed:

- Complete haematology set: Hb, leucocytes/white blood cells (WBC), erythrocytes/RBC, haematocrit, platelets, neutrophil granulocytes, lymphocytes, monocytes, eosinophils, basophils, mean corpuscular haemoglobin (MCH), mean corpuscular volume (MCV), mean corpuscular haemoglobin concentration (MCHC), and reticulocyte count
- Biochemistry:
 - *S*-ferritin
 - TSAT
 - Aspartate aminotransferase (ASAT), alanine aminotransferase (ALAT)

Laboratory tests taken at visit 6 of the lead-in trials P-Monofer-IDA-03 and P-Monofer-CKD-04 will be considered as screening values for the extension trial if they are collected \leq 14 days before the screening visit.

7.10.2 Safety Laboratory Assessments

The following safety laboratory assessments will be analysed:

- Complete haematology set: Leucocytes/WBC, erythrocytes/RBC, haematocrit, platelets, neutrophil granulocytes, lymphocytes, monocytes, eosinophils, basophils, MCH, MCV, MCHC, and reticulocyte count
- Biochemistry:
 - *S*-sodium, *s*-potassium, *s*-calcium, *s*-phosphate, *s*-urea, *s*-creatinine, *s*-albumin
 - *S*-bilirubin, ASAT, ALAT
 - C-reactive protein (CRP)

7.10.3 Efficacy Laboratory Assessments

The following efficacy laboratory parameters will be analysed:

- Hb
- *S*-ferritin
- TSAT
- *S*-iron

7.11 Adverse Events

AEs will be collected and evaluated for relatedness to trial drug, seriousness, severity, and expectedness. They will be reported to the authorities and followed-up according to local requirements (described in Section 12).

8 TRIAL POPULATION

8.1 Number of Subjects

A target of 100 subjects will be recruited at selected sites with at least 25 subjects from P-Monofer-IDA-01/P-Monofer-IDA-03 and at least 25 from P-Monofer-CKD-04. The distribution of subjects from each of the three trials does not need to be equal and the subjects will be enrolled consecutively based on the enrolment criteria until 100 subjects have been enrolled.

8.2 Inclusion Criteria

A subject will be eligible for inclusion in the trial if he/she fulfils the following criteria:

1. Completed one of the lead-in trials
2. Randomised and dosed with iron isomaltoside in one of the lead-in trials. The dose given needs to be in compliance, i.e. within 80-120 % of the cumulative dose.
3. Having a Hb of ≤ 11 g/dL
4. Screening *s*-ferritin ≤ 100 ng/mL, or ≤ 300 ng/mL if TSAT ≤ 30 %
5. Life expectancy beyond 18 months by Investigator's judgement
6. Willingness to participate and signing the informed consent form (ICF)

8.3 Exclusion Criteria

A subject will not be eligible for inclusion in this trial if he/she fulfils any of the following criteria:

1. IV iron treatment between the lead-in trial and screening
2. During 30-day period prior to screening or during the trial period; has or will be treated with a red blood cell transfusion, radiotherapy, and/or chemotherapy
3. Received an investigational drug within 30 days of screening
4. ALAT and/or ASAT > 3 times upper limit of normal (e.g. decompensated liver cirrhosis or active hepatitis)
5. Undergoing dialysis for treatment of CKD or under consideration for dialysis during the trial period
6. Pregnant or nursing women. In order to avoid pregnancy, women of childbearing potential have to use adequate contraception (e.g. intrauterine devices, hormonal contraceptives, or double barrier method) during the whole trial period and 7 days after the last dosing
7. Any other laboratory abnormality, medical condition, or psychiatric disorders which, in the opinion of the Investigator, will put the subject's disease management at risk or may result in the subject being unable to comply with the trial requirements

8.4 Subject Recruitment

Informed consent must be obtained from the subject before any trial related procedures are carried out.

In obtaining and documenting informed consent, the Investigator should comply with any applicable regulatory requirements, and should adhere to International Conference on Harmonization-Good Clinical Practice (ICH-GCP) and the Declaration of Helsinki.

Before informed consent is obtained the subject should be allowed ample time and opportunity to read the subject information sheet, to enquire about details of the trial, and to decide whether or not to participate.

If the subject wishes to participate, the written ICF should be completed as appropriate and then signed and personally dated by the subject and the Investigator who conducted the informed consent discussions. The procedure for obtaining the informed consent must follow the local requirements and legislation.

9 SUBJECT COMPLETION AND WITHDRAWAL

9.1 Screen Failures

The PI will maintain a list of screening numbers and names of the subjects who have been screened at the site in order to allow for identification of records at a later date. The reasons for failure should be noted in the screening log of the site file and the final visit form.

9.2 Re-screening

If a subject does not fulfil the inclusion/exclusion criteria (screen failure), they may be re-screened up to three times. Each subject re-screened must be re-consented and allocated a new subject number. All required screening assessments must be repeated in accordance with the protocol.

9.3 Subject Withdrawal

The subject has the right to withdraw from the trial at any time and for any reason without prejudice to his/her future medical care by the physician or at the institution. The PI can withdraw subjects from the trial in the following situations; treatment failure, safety reasons, and protocol violations.

The subject may also withdraw the consent if he/she does not wish to or is unable to continue in the trial. The Investigator will discuss with the subject the most appropriate way to withdraw in order to ensure the subject's health. If a subject withdraws from the trial, the Investigator will perform all final visit assessments, besides the scheduled trial assessments for that visit. Upon subject withdrawal, the Investigator will fill in the final visit form including the reason for withdrawal.

A subject who withdraws from the trial will not be re-enrolled or replaced with a new subject.

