1.2 Definition of Terms

Baseline values	The “baseline” values are the values measured at the baseline visit, before first administration of the trial drug. For variables/assessments not performed on the baseline visit, the baseline value is the value from the screening period measured closest to the baseline visit.
Completed subject	A subject, who is enrolled in the trial after signing informed consent, exposed to trial drug, and not withdrawn or lost to follow up during the trial.
End of trial	The end of trial is the last subject last visit date.
Final subject visit	The final trial visit for a subject. No trial related procedure is performed after this visit.
Iron isomaltoside	Iron isomaltoside 1000 (Monofer [®])
Subject withdrawal	Time point when the subject exits from the trial prior to the planned completion of all trial drug administrations or assessments.
Screening period	The time period from signed informed consent until inclusion or exclusion from the trial.

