5.2 Secondary Safety Endpoints

The secondary safety endpoints are the following:

- Serious or severe hypersensitivity reaction starting on or after the treatment with iron isomaltoside (i.e. treatment-emergent). The hypersensitivity terms are defined as standardised Medical Dictionary for Regulatory Activities query (SMQ) terms (including four additional terms) in Appendix A.
- Composite cardiovascular adverse events (AEs) starting on or after the treatment with iron isomaltoside (i.e. treatment-emergent). The adjudicated composite AEs includes the following:
 - Death due to any cause
 - Non-fatal myocardial infarction
 - Non-fatal stroke
 - Unstable angina requiring hospitalization
 - Congestive heart failure requiring hospitalization or medical intervention
 - Arrhythmias
 - Hypertension
 - Hypotension

The AEs will be adjudicated by an independent clinical events classification committee (described in a separate adjudication charter). The specified definition of adjudicated endpoints is given in Appendix B.

- Time to first composite cardiovascular safety AE
- Serum (*s*-) phosphate < 2 mg/dL at any time from baseline to month 6

In addition, physical examinations and measurements of vital signs, height, weight, electrocardiogram (ECG), and safety laboratory parameters will be measured as part of standard safety assessments.

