10.2 Dosage, Administration and Blinding of Trial Drug

Subjects will be dosed with a single infusion of 1000 mg iron isomaltoside diluted in 100 mL 0.9 % sodium chloride and given over approximately 20 minutes. No test dose will be applied.

No premedication (e.g. antihistamine or steroids) is allowed before administration of the trial drug. If the subject is in daily treatment for e.g. allergy or asthma this is not considered as "premedication" and may be continued.

Trial ID: P-Monofer-IDA/CKD-EXT-01

Protocol Version: 2.0 (amendment 1)

Date of Document : 14 June 2017

The subjects must be observed for signs and symptoms of hypersensitivity during and after trial drug administration for at least 30 minutes and until clinically stable following completion of each administration.

Details of administration and storage of iron isomaltoside are further described in the Drug Handling Plan.

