12.4 Collection of Adverse Events

The Investigator is responsible for ensuring that all AEs (as defined in Section 12.1) observed by the Investigator or reported by the subject are properly collected and recorded in the subject’s medical record as well as in the AE pages of the eCRF.

Screen failures: All SAEs will be reported in the eCRF from the time a subject has signed the ICF and until he/she exits the trial. Non-serious AEs occurring in subjects who are never treated with the trial drug will not be collected.

Treated subjects: From the time a subject has signed the ICF and until he/she exits the trial, all AEs/SAEs will be reported in the eCRF. AEs/SAEs occurring before administration of the trial drug are considered as non-treatment emergent, and those occurring after administration of the trial drug are considered as treatment emergent.

If a subject is permanently withdrawn from the trial because of an AE, this information must be included in the final visit form.

An AE should be described in the following manner: The nature of the event will be described in precise, standard medical terminology (i.e. not necessarily the exact words used by the subject). If known, a specific diagnosis should be stated. Furthermore, the Investigator should describe an AE regarding seriousness (see Section 12.2), severity, relatedness, action taken, and outcome.

Severity

- Mild: The AE does not interfere in a significant manner with the subject's normal functioning level, but may be an annoyance
- Moderate: The AE produces some impairment of functioning but is not hazardous to health, but is uncomfortable and/or an embarrassment
- Severe: The AE produces significant impairment of functioning or incapacitation and is a hazard to the subject

Relatedness

- Related: The AE is related to the medicinal product
- Possible related: A causal relationship is conceivable and cannot be dismissed
- Unlikely related: The event is most likely related to an aetiology other than the medicinal product
- Not related: No relatedness to the medicinal product

The categories "related" and "possible related" will be classified as related AEs and the categories "unlikely related" and "not related" will be classified as unrelated AEs in the clinical study report (CSR).

Outcome

- Recovered/resolved: Complete clinical recovery without any sequel attributable to the event as per Investigator's discretion

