12.5 Reporting of SAEs

The Investigator must report all SAEs promptly and within **24 hours** to Drug Safety at Pharmacosmos A/S after obtaining knowledge of the event.

The Investigator should report the SAEs by filling out the SAE form and report to Pharmacosmos A/S either by e-mail at **[contact]** or **[contact]**.

Contact details: Drug Safety, Pharmacosmos A/S
[name]
Phone: +
[contact]
E-mail: [contact]

After the initial SAE report, the Investigator is required, proactively, to provide further information regarding the subject's condition. All follow-up information must be forwarded to Pharmacosmos A/S as it becomes available.

For all AEs with fatal outcome, autopsy reports (if available) and relevant medical reports should be reported to Pharmacosmos A/S, as described above.

SAEs occurring after trial termination must be reported if considered related to the trial treatment.

Pharmacosmos A/S will report SUSARs to the Competent Authorities within 7 calendar days for fatal and life threatening SUSARs and follow-up information within the next 8 calendar days. All other SUSARs are submitted as soon as possible within 15 calendar days and relevant follow-up information is subsequently communicated as soon as possible.

Pharmacosmos A/S will inform any SUSARs to all PI(s) within 15 calendar days by circulating the Council for International Organizations of Medical Sciences (CIOMS-I) form.

All SAEs including expected SARs will be reported by Pharmacosmos A/S to the Competent Authorities by the annually Development Safety Update Report.

In addition, 6-monthly safety reports will be prepared by Pharmacosmos A/S and submitted to the Investigators for information.

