13 PREGNANCIES

Subjects who become pregnant during the trial should continue the trial but cannot receive more trial drug. Thus, the subjects may attend visit 3, 4, and 5.

If a subject becomes pregnant during the trial, they will be required to inform the Investigator about the pregnancy, delivery, and the health of the infant until 1 month of age. The Investigator must report the pregnancy and follow-up within 14 calendar days of obtaining the infor-

mation. Pregnancy complications must be recorded as an AE. If the infant has a congenital anomaly/birth defect, this must be reported and followed up as an SAE.

The site will send a copy of the pregnancy form to Pharmacosmos A/S within 1 working day to Drug Safety, contact details in Section 12.5.

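### Investigator withdrawal of a dosed subject ends collection of new safety events before month 6, so crude incidences of later events are biased low

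*Protocol*

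**What the plan says.** Protocol 9.3 gives the investigator a discretionary right: "The PI can withdraw subjects from the trial in the following situations; treatment failure, safety reasons, and protocol violations". It is not limited to the period before dosing. Protocol 1.2 defines withdrawal as "Time point when the subject exits from the trial prior to the planned completion of all trial drug administrations or assessments", and no separate status exists for a subject who is off treatment but still observed.

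For treated subjects, Protocol 12.4 sets the collection window: "From the time a subject has signed the ICF and until he/she exits the trial, all AEs/SAEs will be reported in the eCRF". Protocol 12.5 adds: "SAEs occurring after trial termination must be reported if considered related to the trial treatment".

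Treatment is given once (Protocol 10.2): "Subjects will be dosed with a single infusion of 1000 mg iron isomaltoside". Visits 3 to 5 carry assessments only, and the last is at month 6 (Protocol 6.7): "Visit 5 will be conducted 26 weeks" after baseline.

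Two of the safety endpoints in Protocol 5.2 depend on the whole period. The composite cardiovascular endpoint includes "Death due to any cause", and low phosphate (below 2 mg/dL) counts at any time up to month 6.

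SAP 5.1 takes the number of subjects in the analysis set as the denominator for percentages and uses observed cases without imputation. SAP 7.3.1 censors time to first composite cardiovascular event at the last attended visit, whatever the reason for leaving.

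**The concern.** The primary objective is safety after re-dosing, with six months of follow-up. After the infusion, taking part means being observed, so withdrawing a dosed subject has one effect on the trial: observation stops. At least one of the permitted grounds, safety, is plausibly linked to the risk of later events.

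The protocol already accepts follow-up without further drug in another setting. Protocol 13 says: "Subjects who become pregnant during the trial should continue the trial but cannot receive more trial drug", and allows these subjects to attend visits 3 to 5. There is no matching provision for subjects whom the investigator withdraws.

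At stake are the later drug reaction counts, the composite cardiovascular count, the time-to-event curve and the phosphate endpoint. The analysis cannot recover events that were never collected.

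**Working it through.** **What is and is not captured after investigator withdrawal**

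| Item | Captured? | Source |
|---|---|---|
| The event that led to withdrawal | Yes | Protocol 12.4 |
| One set of final-visit assessments | Yes; written for a subject who withdraws, so its use for investigator withdrawal is implied | Protocol 9.3 |
| Outcome of events already recorded | Yes, as far as possible | Protocol 12.4 |
| New related serious events | Possibly; the text refers to trial termination, which may not mean one subject's exit | Protocol 12.5 |
| New non-serious drug reactions | No | Protocol 12.4 |
| New unrelated cardiovascular events or deaths | No | Protocol 12.4 |
| Phosphate after exit | No | Protocol 6.5 to 6.7 apply only while the subject is in the trial |

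**Effect on the two estimators**

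- Crude percentage: a withdrawn subject with no recorded event stays in the denominator and counts as event-free to month 6. The percentage is low even if withdrawal is unrelated to risk.
- Kaplan-Meier: the subject leaves the risk set at exit. The estimate is low only if withdrawn subjects have a higher later hazard than those who stay.

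**Size**

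The plan has no figure to reproduce. N = 100 (Protocol 8.1) and 26 weeks (Protocol 6.7) come from the documents. Everything else is assumed.

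Follow-up lost with n withdrawals at week 6 = n × (26 − 6) / (100 × 26). For n = 5, 10 and 15 this is 3.8%, 7.7% and 11.5%.

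Events missed: assume 10 of 100 are withdrawn at week 6, a 26-week composite risk of 6.5% in stayers, and a constant hazard that is equal in all subjects up to exit.

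- Weekly hazard h = −ln(1 − 0.065) / 26 = 0.002585.
- Risk to week 6 = 1 − exp(−6h) = 1.54%.
- Captured = 90 × 0.065 + 10 × 0.0154 = 6.00 subjects with an event.
- Missed = 10 × (1 − 0.0154) × [1 − exp(−20 × k × h)], where k is the hazard ratio after exit.

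| k | Later risk in withdrawn | Missed | True per 100 | Crude | Kaplan-Meier | Share missed |
|---|---|---|---|---|---|---|
| 1 | 5.0% | 0.50 | 6.50 | 6.0% | 6.5% | 7.6% |
| 2 | 9.8% | 0.97 | 6.97 | 6.0% | 6.5% | 13.9% |
| 4.3 | 19.9% | 1.96 | 7.97 | 6.0% | 6.5% | 24.6% |

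With 5 withdrawals and k = 2, captured = 95 × 0.065 + 5 × 0.0154 = 6.25 and missed = 0.48, so 7.2% are missed.

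For scale, the exact 95% Clopper-Pearson limits for 6 of 100 are 2.2% to 12.6%.

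**The case against.** The strongest reply has five parts.

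1. **Not every ground is outcome-related.** A protocol violation is not an outcome, and the documents do not link treatment failure to cardiovascular events or drug reactions. This stands: informative withdrawal is plausible for the safety ground and less clear for the other two. It does not rescue the crude percentages, which are low in any case.

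2. **The primary endpoint is largely protected.** SAP 7.1 puts its confidence limits on the number of subjects with a drug reaction, so a subject withdrawn for a reaction is already in the numerator. This stands. SAP 7.3.1 also rules out relatedness to the lead-in dose after more than five half-lives. By the same reasoning, reactions starting late after a single infusion may be few. That is an inference, but a fair one.

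3. **A reader might infer that all safety data stop at withdrawal.** The documents do not support that, since Protocol 9.3, 12.4 and possibly 12.5 keep part of the data. What is lost is new events after exit.

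4. **A reader might take a quarter of events missed as the expected loss.** That figure needs about a 4.3-fold rise in hazard exactly at exit, with no excess before it. Subjects withdrawn for safety would be expected to have some excess earlier, when events are captured.

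5. **Later events are harder to interpret.** After withdrawal the subject receives standard hospital care (Protocol 9.5), which may include treatments prohibited in the trial. This is a real trade-off. It is a reason to record that care, not a reason to leave the events uncollected.

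**Conclusion.** The point holds in a limited form. Read together, Protocol 1.2, 9.3 and 12.4 end collection of new adverse events when the investigator withdraws a dosed subject, and the existing safeguards do not cover new events up to month 6.

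Crude incidences of the composite, of low phosphate and of later drug reactions are biased low whenever such withdrawals occur. The bias in the Kaplan-Meier curve depends on withdrawal being informative. The subject-level drug reaction percentage is little affected when the withdrawal was itself for a reaction.

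The size is unknown because the documents give neither withdrawal nor event rates. Under the stated assumptions, 10 withdrawals at week 6 lose about 8% to 25% of composite events. In absolute terms that is 0.5 to 2.0 subjects per 100, well inside the sampling error, and it shrinks if withdrawals are few. In a descriptive trial with no hypothesis test this overturns no decision, but it is an avoidable loss on the trial's main question and should be corrected.

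**What to change.** - **Protocol 9.3:** separate ending trial treatment from ending follow-up. State that investigator withdrawal does not by itself end safety data collection for a dosed subject who has not withdrawn consent to follow-up.
- **Protocol 12.4:** for these subjects, collect adverse events, serious adverse events, composite cardiovascular events and vital status to day 182 (26 × 7), at visits 3 to 5 or by contact or record check. Collect phosphate where those visits are attended. Record the care received after withdrawal.
- **Protocol 12.5:** say whether trial termination includes one subject's exit.
- **SAP 7.3.1:** censor time to first composite cardiovascular event at the end of this follow-up instead of the last attended visit.

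The cost is amendment wording and a few more contacts. Visits 3 to 5 are already scheduled, but record checks and vital-status contacts would be new procedures. Some later events will be harder to attribute to the trial dose, and reported event rates may be slightly higher. Clinical care, the grounds for withdrawal and the subject's right to leave are unchanged.
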